7.0 STUDY INTERVENTION (Device or Other Intervention)

- **Description:** Subjects will receive intermittent theta burst TMS, consisting of a 50 Hz triplet burst at 5 Hz for 2 seconds per train, with an inter-train interval of 200ms, followed by 8 seconds rest, for 600 total pulses per treatment.
- **Receipt/Storage:** The machine used for the study is routinely used for regular care at a UNC outpatient clinic and is regularly maintained and calibrated.
- **Packaging/Labeling:** N/A
- **Dosing:** Patients will be treated at 120% of resting Motor Threshold as determined by standard methods. The treatment will be provided at UNC's outpatient clinic where TMS is routinely provided. TMS Treatment will be provided daily Monday-Friday for 4 weeks, for a total of 20 sessions.
- **Drug Return/Destruction:** N/A
- **Drug Accountability:** N/A

The TMS apparatus consists of the following, the description and use of which is found in the device description.

- Treatment Coil
- Motor Threshold Coil
- TMS stimulator
- Chair with positioning arm

8.0 STUDY INTERVENTION ADMINISTRATION

Treatment compliance and Adherence: A medication review will be performed prior to each treatment administration for treatment compliance. If 20% of planned sessions are missed, contraindicated medications are used, or there is worsening or lack of benefit, investigators can remove subject from the study. A trained study clinician will do administration of treatment.

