4.6 Rescue medication administration: N/A

4.7 Subject Completion / Withdrawal procedures

Subjects who complete the study will be reminded of the study team's contact information should they have any questions in the future. Files will be kept under lock and key in a locked office in a secure facility for the

required amount of time according to GCP (Good Clinical Practice) principles and FDA regulations. For those wishing to withdraw from the study early, a termination visit will be scheduled to ensure safety, proper follow up, review adverse effects, and medications. CDRS-R, HAM-D, all cognitive, and safety assessments will be performed for final data capture if the patient agrees.

Patients will be withdrawn by investigators if they miss 20% of planned treatments, for noncompliance, or any other issues the PI determines can cause harm to the patient.

We will not replace discontinued participants. We will use the data we have up until discontinuation.

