6.3 Statistical Methods

- **Baseline Data:** CDRS-R, HAM-D, and other cognitive and safety assessments will be used at screening to capture baseline data.
- **Efficacy Analysis:** As this is an uncontrolled study design, the investigators understand that any change in scores or observed improvement in symptoms may not be necessarily attributable to the treatment received. Thus, efficacy analysis will be described in this context. The investigators feel that a larger study would be indicated which may be sham controlled. Repeated measures ANOVA will be used to compare depression rating scores from each of the treatment weeks compared to baseline, as well as comparing scores between follow up visits and baseline and end of treatment weeks. Pearson's r coefficient will be used to determine correlation between, CSSR-S scores, and primary endpoints (CDRS-R & HAM-D). Descriptive statistics to identify if NSSIB is present since the subject's last visit at baseline, during the interventional period and follow ups, will be used. It is worth noting that use of ANOVA analysis has been recommended by a biostatistician, but due to a small sample size, longitudinal data will not have adequate statistical power. In addition, confidence intervals will be large and results will be uninformative regarding statistical power. This uncertainty may contribute to a future study sample size that is still too small for statistical power, but a larger sample size than this protocol.
- **Pharmacokinetic Analysis:** N/A
- **Safety Analysis:** Measurement of safety is a continuous process starting with screening. Medical review of symptoms occurs at every visit. In addition, should safety concerns related to study treatment occur, additional unscheduled safety visits can be performed. Additional assessments are done weekly during the 4-week treatment phase.
- **Personnel:** Study coordinator will complete data entry into RedCap system and oversee data management. The Principle Investigator will do oversight. A TraCS biostatistician ([name]) will complete data analysis and computations and will work with the study team throughout the duration of study activities and completion.

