Appendix B: TIME AND EVENT SCHEDULE

Time and Event Schedule	Screening	Weeks 1-4 Treatment*g					Follow up**		
Study tasks	V1 (1 wk period)	V2b ; V7, V12, V17	V3, V8, V13, V18	V4, V9, V14, V19	V5, V10, V15, V20	V6, V11, V16, V21	V22^c	V23^d	V24^d
Informed consent***	x								
CDRS-R***	x					x	x	x	x
HAM D ***	x					x	x	x	x
SCID-5***	x								
MSSE	x					x	x	x	x
Trails B	x					x	x	x	x
List Generation	x					x	x	x	x
NSSIB interview & SITBI	x					x	x	x	x
C-SSRS	x					x	x	x	x
UDS ^a	x								
Urine pregnancy test ^a	x								
Vitals (HR, RR, O ² , BP, temp, weight ^h)	x ^h	x	x	x	x	x ^h	x ^h	x ^h	x ^h
Physical exam ***	x						x	x	x
AE review ^h ***	x	x	x	x	x	x	x	x	x
Medication review ***	x	x	x	x	x	x	x	x	x
Satisfaction Questionnaire									x
Neurological exam***	x								
iTBS ^f ***		x	x	x	x	x			

Footnotes

a: Can be done anytime at investigator discretion for safety purposes, predose on any treatment day.

b: Treatment should start by the following business day, within 7 days of screening.

c: 1 week after last treatment.

d: 4 weeks after last treatment.

e: 12 weeks after last treatment.

f: First day of treatment will determine motor threshold

g: Will include change in pregnancy status (OHRE SOP 4801, re: verbal assessments for treatments w/o known teratogenic effects)

h. Weight also collected as planned timepoint – per investigator discretion can also be obtained at any time during participation

*: To be done Monday-Friday, can start any day of the week.

**: +/- 3 days

***: M.D. must be present and/or perform tasks.

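### Subjects removed for worsening or lack of benefit have no planned 12-week rating, so the 12-week change from baseline can over-represent improvers (minor; cheap to fix)

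*Combined protocol and SAP*

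**What the plan says.** Section 8.0 makes an outcome-related removal possible: if "there is worsening or lack of benefit, investigators can remove subject from the study". The wording is permissive, and what the subject leaves is the study.

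Section 4.7 lists different grounds in firmer language: "Patients will be withdrawn by investigators if they miss 20% of planned treatments", for noncompliance, or for "any other issues the PI determines can cause harm to the patient". Lack of benefit is not listed there; worsening might fall under the harm ground. Discontinued subjects are not replaced, and "We will use the data we have up until discontinuation".

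Section 4.7 does provide an exit visit: "For those wishing to withdraw from the study early, a termination visit will be scheduled". At that visit, "CDRS-R, HAM-D, all cognitive, and safety assessments will be performed for final data capture if the patient agrees". The text does not say whether this covers subjects whom the investigators remove.

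CDRS-R and HAM-D are rated weekly from the fifth treatment day (section 4.2) and at 1, 4 and 12 weeks after treatment (section 4.3). Appendix B dates the last visit as "12 weeks after last treatment". Neither section 4.3 nor Appendix B provides for rating someone who left early.

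Durability is Hypothesis 2 of Aim 1 (section 2.0) and a secondary endpoint (section 6.2). Section 6.3 plans repeated measures ANOVA, including "comparing scores between follow up visits and baseline and end of treatment weeks". For data that stay missing, section 6.3 promises a clear remark in the results and discussion.

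**The concern.** The ground for removal is the outcome being measured. A subject who is not improving can leave at the investigators' discretion, and after that nothing is planned that could yield a 12-week score. A completed exit visit gives a score at exit, not at week 12. The mean 12-week change from baseline would then describe those who stayed, and staying depends partly on having improved.

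The consequence is limited but real. Section 6.4 says the results may serve as preliminary data for R01 applications, and a durability estimate that leaves out removed non-improvers would be a favourable starting point for planning. The remark promised in section 6.3 tells the reader that data are missing; it does not recover them. Ratings never taken cannot be recovered at the analysis stage.

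**Working it through.** The plan gives no effect size, SD, correlation or dropout rate, and section 6.4 justifies five subjects on logistics and safety. There is no planned figure to reproduce. What follows is an illustration under stated assumptions.

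**Model.** Units are SDs of change, with positive values meaning improvement.
- M is the change from baseline when removal is decided: M ~ N(d, 1).
- X is the 12-week change from baseline: SD 1, correlation r with M. Its mean may be lower than d by a relapse amount, rel, which does not affect the bias among those kept.
- A non-improver has M ≤ 0 and is removed with probability p. The value p = 1 is an extreme reading of a permissive rule.

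**Formulas, among subjects kept.**
- Bias in mean M: B = p·φ(d) / [1 − p·Φ(−d)]
- Bias in mean X: r·B
- Bias in mean (X − M): (r − 1)·B
- Expected removals of five: 5·p·Φ(−d)

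Worked case, d = 0.5 and p = 0.5: B = 0.5 × 0.3521 / (1 − 0.5 × 0.3085) = 0.1760 / 0.8457 = 0.208. With r = 0.8, the bias in the 12-week change is 0.8 × 0.208 = +0.167.

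Results at r = 0.8, for p = 0.25 / 0.50 / 1.00:

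| True change d | φ(d) | Φ(−d) | Bias in 12-week change from baseline (SD) | Expected removals of five |
|---|---|---|---|---|
| 0.5 | 0.3521 | 0.3085 | +0.08 / +0.17 / +0.41 | 0.39 / 0.77 / 1.54 |
| 1.0 | 0.2420 | 0.1587 | +0.05 / +0.11 / +0.23 | 0.20 / 0.40 / 0.79 |
| 1.5 | 0.1295 | 0.0668 | +0.03 / +0.05 / +0.11 | 0.08 / 0.17 / 0.33 |
| 2.0 | 0.0540 | 0.0228 | +0.01 / +0.02 / +0.04 | 0.03 / 0.06 / 0.11 |

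**Week 12 against end of treatment.** If removal is judged on the end-of-treatment score, the bias is (0.8 − 1)·B: −0.02 / −0.04 / −0.10 at d = 0.5 and −0.01 / −0.03 / −0.06 at d = 1. It runs against persistence, and is zero at r = 1.

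**A second removal model.** Suppose the least improved of five is lost with certainty. The expected minimum of five standard normal values is about −1.16, so the mean of the other four rises by 1.16 / 4 = 0.29 SD on average at correlation 1, and by 0.8 × 0.29 = 0.23 SD at correlation 0.8. This is an average; a single realised trial can show more or less.

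**Yardstick.** The 95% confidence interval half-width at n = 5 and SD 1 is t(0.975, 4 df) / √5 = 2.776 / 2.236 = 1.24 SD. The largest entry in the table is 0.41 / 1.24 = 33% of this; the smallest is about 1%.

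**Carrying the exit score forward.** The bias in the mean over all five is p·[rel·Φ(−d) − (1 − r)·φ(d)]. At d = 0.5, r = 0.8, p = 1: rel = 0 gives −0.2 × 0.3521 = −0.070; rel = 0.5 gives 0.5 × 0.3085 − 0.0704 = +0.084. The sign changes at rel = 0.0704 / 0.3085 = 0.23 SD, so this device is not a lower bound.

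**The case against.** The plan has safeguards. Weekly ratings mean that a subject removed after the first week normally has a score from within about a week, with or without an exit visit. Aim 3 counts withdrawals: feasibility fails if more than one of five leaves iTBS for intolerable side effects or persistent symptoms, and also if any subject completes fewer than 15 sessions. Section 9.0 stops the study on a suspected pattern of lack of efficacy. Sections 6.3 and 10.4 require the reason for missing data to be recorded, and section 6.3 already cautions about attribution to treatment and about wide intervals. With five subjects, every removal will be visible.

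All of this stands, and it keeps the point minor. It limits the loss at end of treatment and makes removals countable, but none of it supplies a 12-week score.

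It is also fair that every input above is assumed and that the bias nearly vanishes if the true change is large.

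Two stronger readings are tempting. A reader might infer that the durability hypothesis as a whole is inflated. The documents do not support this: section 6.3 plans two follow-up comparisons, and the one against end of treatment is not pushed upward by this mechanism. A reader might also infer that a removed subject disappears from every time point, because a complete-case repeated measures ANOVA would do that. The plan does not specify such an analysis, and section 4.7 says data up to discontinuation are used.

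**Conclusion.** The point holds as a minor one. Following the plan as written can lose non-improvers from the 12-week change from baseline, and the mean of those who remain can be too favourable. Under the assumed inputs the bias runs from +0.01 SD (true change 2 SD, a quarter of non-improvers removed) to +0.41 SD (true change 0.5 SD, all removed). This is smaller than the uncertainty with five subjects, but it runs in one direction.

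The conclusion rests on the discretion in section 8.0 actually being used, and on early and 12-week change being positively correlated. It concerns one descriptive comparison within a secondary endpoint of an unpowered pilot. If Hypothesis 2 is read as persistence from end of treatment, it is not inflated.

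Separately, sections 4.7 and 8.0 disagree on whether removal is mandatory or discretionary and on whether lack of benefit is a ground. They must be reconciled; no position is taken here on which is right.

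**What to change.** 1. In sections 4.7 and 8.0, distinguish stopping iTBS from leaving the study for data purposes, without changing any clinical stopping rule. Aim 3 already speaks of withdrawal from iTBS. For every treated subject who stops and agrees, keep the scheduled follow-up CDRS-R and HAM-D, at least the 12-week rating. State the time anchor for these subjects: counted from last treatment, someone who stops after week 2 is rated at week 14 (2 + 12), against week 16 (4 + 12) for completers. Either anchor can be defended if stated.
2. State that the exit CDRS-R and HAM-D also apply to subjects removed by investigators.
3. In sections 6.2 and 6.3, report the 12-week change from baseline for all treated subjects with a 12-week rating, separately from week 12 against end of treatment. List those still missing, with reasons. Do not present an exit score carried forward as a lower bound.
4. Reconcile sections 4.7 and 8.0 on the force and grounds of removal.

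The cost is wording plus a few visits already in the schedule. At the assumed rates, expected removals are 0.03 to 1.54 in the whole study, so at most about 1.5 extra 12-week visits, or 3 × 1.54 = 4.6 visits if all three follow-ups are kept. The downside is that burden on subjects who have stopped, and possibly a less favourable mean change.

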9.0 SAFETY MANAGEMENT

- Our protocol includes multiple safety assessments, which include the MMSE, Trails B, list generation, C-SSCR. In addition, we will be performing a review of systems during each visit, which will include the common adverse effects seen in the literature as described in the side-effects section. [12,24]
- **Hearing:** All subjects will be provided ear plugs to be used during the sessions.
- **Adverse Event/Serious Adverse Event monitoring procedures:** Serious and non-serious AE's will be monitored and documented at every visit. Additional referrals or follow up will be provided on an as-needed basis. See Appendix C for a copy of the UNC template AE log used for documentation.
- **Adverse Event/Serious Adverse Event reporting procedures:** UNC policy will be followed for reporting of serious and non-serious adverse events. If the event is unexpected and related or possibly related to treatment and serious or suggests new/ increased risk, this will be reported to the IRB. Reports of AE's will be made within 24 hours of investigators discovering the reportable event.
- **Medical Emergency procedures:** In the rare event of a medical emergency, the investigators performing iTBS are medically trained to handle the situation. In addition, the location of the study will operate in proximity to UNC emergency department, and 911 can be called for assistance. Investigators and study coordinator are Basic Life Support and CPR (Cardiopulmonary resuscitation) certified.
- **Data Safety Monitoring Plan:** Adverse events will be continuously monitored by investigators and assessed for severity, risk to benefit ratio, causality from study treatment. Study will be stopped if suspected pattern of lack of efficacy or additional risk of harm vs. benefit emerges.

10.0 DATA COLLECTION AND MANAGEMENT

10.1 Monitoring Plan: The PI will monitor response rate and adverse events reporting to the UNC IRB.

10.2 Case report forms: Data will be collected on paper source documents and stored according to GCP guidelines (more specifically listed below section 10.3). Data analysis will be performed by a biostatistician from TraCS. Data will be collected on paper source, stored in a secure closet where study staff only have access to, in a locked office, in a secure building where badges are needed to enter off-hours. This building

location is routinely used for clinical research and clinical care (Medical Wings behind the hospital). A biostatistician has been engaged and we have budgeted for TraCS services to help us with data analysis. Data will be manually entered into REDCap. Data analysis will be completed by a biostatistician.

10.3 How confidentiality will be maintained: Data will be collected on paper source and coded with a subject number. All data and confidential PHI (Protected Health Information) will be locked in a secure cabinet/ closet in a secure office in a secure building routinely used for research and clinical purposes. UNC badges and keys will be needed to access study material by study staff only and those authorized per local and federal regulation. In addition, verbal communication will be done privately behind closed doors as routine care is normally provided. EPIC secure in-basket system will also be used by study staff to communicate privately while maintaining confidentiality.

10.4 Data Quality: Source documents will outline which data to be collected and the Principle Investigator will oversee verification of data entry. Study coordinator and investigators will do metrics that can be verified in medical records (demographics). Data that is missing will have documentation as to why it is missing. Scores of assessments used will be collected and entered into the database to measure each aim. Scores will be verified by at least two study personnel.

11.0 RECRUITMENT STRATEGY

5 outpatients will be recruited through either referrals of local psychiatric clinics, including UNC's outpatient psychiatry clinic. Additionally, advertisements will be used to recruit patients who may not have routine treatment at UNC or have a provider referring them.

12.0 CONSENT PROCESS

12.1 Procedure that will be used to obtain informed consent/HIPAA authorization and assent: Parental consent, assent, and HIPAA (Health Insurance Portability and Accountability Act) authorization will be used. A consent checklist/documentation form will be used to ensure all aspects of informed consent are properly obtained.

12.2 Who will obtain consent/assent: Consent will be performed by a study member, licensed clinician experienced in iTBS treatment in order to answer all questions regarding safety, risks, and benefits of study treatment. A study coordinator will also plan to be present to document the consenting process. Paper consent, assent, and HIPAA forms will be obtained and copies will be provided to the subjects as well as placed in medical records. Original copies will be placed in the study record with subject's source documents (subject binders).

12.3 Where consent /assent process will take place: Consent and assent will take place in a private room for confidentiality purposes. The space utilized for this is routinely used for research purposes at UNC.

12.4 How investigator will assure that subjects comprehend the nature of the study, procedures, the risks and benefits: Patients and parents/guardians will be encouraged to ask any questions about the study procedures, and confirm that both parties understand requirements for participating, risks, and benefits. Participants will be reminded that participation is always voluntary and encouraged to do their own research on the topic and discuss with friends/ family as needed.

13.0 PLANS FOR PUBLICATION

We intend to publish the results as a letter to the editor in a peer reviewed medical journal.

15.0 APPENDIX

Appendix A: PROHIBITED MEDICATION LIST

Antidepressants	Tricyclic antidepressants are not allowed 7 days prior to screening. Investigator discretion for all antidepressants
Benzodiazepines	Not allowed 7 days prior to screening
Stimulants	Investigator discretion, may need to be stopped 7 days prior to study treatment.
Antipsychotics	Investigator discretion, may need to be stopped 7 days prior to study treatment.
Antiepileptic	Not allowed if taken for Central Nervous Disorder (such as epilepsy or to lower seizure threshold).

Appendix B: TIME AND EVENT SCHEDULE

Time and Event Schedule	Screening	Weeks 1-4 Treatment*g					Follow up**		
Study tasks	V1 (1 wk period)	V2b ; V7, V12, V17	V3, V8, V13, V18	V4, V9, V14, V19	V5, V10, V15, V20	V6, V11, V16, V21	V22^c	V23^d	V24^d
Informed consent***	x								
CDRS-R***	x					x	x	x	x
HAM D ***	x					x	x	x	x
SCID-5***	x								
MSSE	x					x	x	x	x
Trails B	x					x	x	x	x
List Generation	x					x	x	x	x
NSSIB interview & SITBI	x					x	x	x	x
C-SSRS	x					x	x	x	x
UDS ^a	x								
Urine pregnancy test ^a	x								
Vitals (HR, RR, O ² , BP, temp, weight ^h)	x ^h	x	x	x	x	x ^h	x ^h	x ^h	x ^h
Physical exam ***	x						x	x	x
AE review ^h ***	x	x	x	x	x	x	x	x	x
Medication review ***	x	x	x	x	x	x	x	x	x
Satisfaction Questionnaire									x
Neurological exam***	x								
iTBS ^f ***		x	x	x	x	x			

Footnotes

a: Can be done anytime at investigator discretion for safety purposes, predose on any treatment day.

b: Treatment should start by the following business day, within 7 days of screening.

c: 1 week after last treatment.

d: 4 weeks after last treatment.

e: 12 weeks after last treatment.

f: First day of treatment will determine motor threshold

g: Will include change in pregnancy status (OHRE SOP 4801, re: verbal assessments for treatments w/o known teratogenic effects)

h. Weight also collected as planned timepoint – per investigator discretion can also be obtained at any time during participation

*: To be done Monday-Friday, can start any day of the week.

**: +/- 3 days

***: M.D. must be present and/or perform tasks.

APPENDIX C: ADVERSE EVENT LOG

ADVERSE EVENT Make a separate entry for: ➤ All new adverse events ➤ All AEs with increased severity ➤ All AEs with changes in study drug relationship ➤ All medical conditions present at study drug initiation which have worsened	✓ if AE meets definition of serious*	Grade / Intensity Asymptomatic Mild Moderate Severe	Start Date	End Date	Relationship to study intervention Related Possibly Not Likely Not Related	Was Action Taken? (Circle One) Yes/No	Action(s) Taken^:	Outcome: Recovered Not Recovered Recovered w/Sequelae Fatal Unknown	PI Initials / Date
----------------------------------------------------------------------------------------------------------------------------------------------------------------------------------------------------------------------------------------------------------------------------	--------------------------------------------	--------------------------------------------------------------------	---------------	-------------	----------------------------------------------------------------------------------------------	------------------------------------------------	----------------------	---------------------------------------------------------------------------------------	-----------------------
